## Method of intervention received by the intervention group

The patients assigned to the intervention group will be given a plastic cup of uniform size, along with a twenty four hour fluid chart. These patients will be instructed to use the cup for drinking any form of fluid they wish to consume for the duration of their participation in the study. Verbal instructions will be given on how to fill in the various details required on the fluid chart regarding their oral fluid consumption.

This will be done over the next twenty four hours or until they come for their next follow-up consultation at the clinic. If the next clinic follow-up will be given at the interval of a few days after the preceding consultation, then the researcher or the trained research assistant will provide enough fluid chart forms for the patient to fill until the next consultation.

The patient will be instructed to write down the amount of fluids they drank according to the time that they consumed the fluids in the second column. The patients will be instructed to record the type of fluids they drink in the third column. The patient will only fill the last column if they received any intravenous fluid drip over the next twenty four hours. They are to record the amount of bottles of fluid they receive intravenously.

# Blinding

There will be no blinding done for this pilot study. The blinding process is not possible in the intervention and assessment process because the intervention tool as well as the dengue home care card require verbal explanations to be given to participants. Thus, the research team members and the participants will not be blinded in the intervention and assessment process.

# **Data collection**

The demographic, clinical and laboratory data will be collected accordingly. Refer to the Figure 2 for a flow diagram for the data collection process and to appendix 2 for the data collection form.

# Follow-up

## Duration

All the patients recruited into the study will be followed up until they are clinically better and/or their laboratory markers show improvement as assessed by the respective doctors. Thus, different patients will be followed-up for different lengths of time.

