# **Study population: Participants**

Inclusion criteria

All patients with the following:

[figure not shown]
- 1) Patients who are suspected to have dengue fever from the history and examination findings by a primary healthcare clinician.
- 2) History of fever for three days or more.
- 3) Thrombocytopenia: Platelets equal to or less than  $150 \ge 10^9$ /l.
- The platelet level of 150 x 10^9/L is chosen as the highest cut off point for thrombocytopenia because it is the lowest level of the normal range for platelets according to the University of Malaya Medical Centre's clinical laboratories. During the early febrile illness, the platelets and total white blood cell count are found to be lower among patients with dengue compared with patients with other febrile illness.
- 4) Age equal to or more than 12 years old. This is arbitrarily set to ensure that the patient concerned can understand instructions and fill in the fluid chart reliably and independently.

[figure not shown]

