## Method of recruitment

#### Screening

All the patients presenting to the clinic with a history of fever for 3 days duration or more will be identified by the triage counter nurses. The clerk at the registration desk who handles the allocation of the patients to the various doctors working in the clinic for that working day would provide the following details on a separate list: the patient's name, registration number, identification card number and details as to which doctor's room the patient has been allocated to.

It is standard practice for the clinic that such patients would have a full blood count test done (blood is drawn by the respective nurses) mostly before the patient's consultation with their doctors. Since results of clinical investigations of patients are available online, either the researcher or the assistants would then trace the full blood count results from the computer. This will be done using the details provided on the daily working list which was mentioned earlier.

For patients with platelet counts of equal to or less than 150 x 10^9g/L, the researcher or the assistants will then find and tag the patient's clinic card and clinical notes in the various consultation rooms with a red tag. They will also remind the doctor who would be attending to the patient to re-direct the patient to the researcher's booth after the patient's consultation has ended if they suspected that the patient might have dengue fever, and if they were going to give the patient another appointment for outpatient monitoring.

The tag placed with the patient's clinic card also serve as a reminder for the attending doctors to redirect the patient to the researcher's booth after each subsequent follow-up consultation. This will be continued until the attending doctor is satisfied that the patient has completely recovered from the febrile illness either by clinical assessment or laboratory markers.

Thus the initial assessment of these patients and the subsequent follow-up consultations will be done by the various doctors working at the primary health clinic first. The researcher and the trained research assistants see the patients after the clinic consultation with their respective doctors had finished.

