## Defaulter tracing

For those who does not turn up for the follow-up with the researcher or the trained research assistants, an attempt will be made to contact the patient via the telephone, with a maximum of three attempts. During the telephone consultation, either the researcher or the trained assistant will attempt to find out the reason why the patient did not come for the follow-up appointment that was given. The patient will then be asked whether they will be amenable to come for follow-up the next day or at the next nearest date when convenient.

If the patient did not come for follow-up as he or she has been admitted to hospital, then details regarding the admission will be obtained. Such details will include which hospital they have been they admitted to, the date of admission, the reason for the admission and who recommended for the admission i.e. was it by medical personnel or did the patient themselves request for the admission. All these details would be entered on the standardized data collection form.

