## Dengue phase of illness

The dengue phase of illness is based on the day of illness on recruitment into the study, which is as follows:

- The febrile phase is defined as day 1 of illness till day 3 of illness.
- The critical phase is from day 4 of illness to day 6 of illness.
- The recovery phase is defined as from day 7 onwards of illness.

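### Hospitalisation has no common observation window and no described check after release from follow-up, so later admissions may be missed

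*Protocol*

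**What the plan says.** **End of follow-up.** Under Follow-up, Duration, patients are "followed up until they are clinically better and/or their laboratory markers show improvement as assessed by the respective doctors", and as a result "different patients will be followed-up for different lengths of time". Under Method of recruitment, Screening, patients are sent back to the research booth after each visit "until the attending doctor is satisfied that the patient has completely recovered from the febrile illness either by clinical assessment or laboratory markers". Neither section sets a minimum day of illness.

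**Illness days.** Inclusion criterion 2 is "History of fever for three days or more". Exclusion criterion 4 removes anyone without a booked review. The fluid chart instructions allow for a next visit after 24 hours or after a few days. Under Dengue phase of illness, "The critical phase is from day 4 of illness to day 6 of illness"; the same section says that "The dengue phase of illness is based on the day of illness on recruitment into the study".

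**Finding admissions.** Defaulter tracing begins "For those who does not turn up for the follow-up with the researcher or the trained research assistants". It allows up to three telephone attempts. If admission was the reason for the missed visit, the hospital, date, reason and source of the recommendation are recorded. The Tracing section covers online blood counts and, a week after testing, dengue serology. It does not mention admissions.

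**Use of the outcome.** Preliminary outcome measures lists hospitalisation first and need for intravenous fluid second, both assessed at the close of the two-month collection period. Under Assumptions, any admission after recruitment is taken to imply a drip. Statistical analysis compares categorical outcomes by chi-squared or Fisher's exact test. Estimated sample size says that the effect size found will feed the main trial's calculation.

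**The concern.** A crude proportion hospitalised is comparable between patients and arms only if everyone is observed for the same period, or if unequal observation is allowed for. Here the treating doctor's view that the patient is improving ends observation, in a trial without blinding. That view could be affected by knowledge of the allocated arm.

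Once released, a patient has no appointment to miss, so the telephone procedure is not triggered. Because that procedure asks which hospital admitted the patient, the plan itself expects some admissions elsewhere.

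At stake are the two hospitalisation rates and their difference, which are meant to inform the size of the main trial. Intravenous fluid need inherits the gap, since it is inferred from admission. The other described record of it, the last column of the fluid chart, exists only in the intervention arm, and charts are renewed only while another appointment is given.

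**Working it through.** **1. The plan's own figure.** The minimum size is 30 per group, 2 × 30 = 60. No event rate, effect size or power is given, so there is no power calculation to reproduce.

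**2. Can release fall within illness days 4 to 6?** Day 1 is the day of fever onset, so three days of fever puts the earliest entry at about day 3. Because a review visit is required for entry, the earliest release is day of recruitment + interval to the next visit.

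| Recruited on day | Interval 1 day | 2 days | 3 days |
|---|---|---|---|
| 3 | day 4 | day 5 | day 6 |
| 4 | day 5 | day 6 | day 7 |
| 5 | day 6 | day 7 | day 8 |

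Six of these nine combinations fall within days 4 to 6. Release on day 4 leaves days 5 and 6 unobserved. The table shows what the rules permit, not how often it happens.

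**3. What would reveal a later admission?** The telephone call needs a missed visit. The online trace is for blood counts and serology. No visible section describes a contact or record check after release. A released patient who comes back to the clinic with fever could be picked up again at triage; one admitted without passing through the clinic has no described route into the data.

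**4. Effect of equal loss.** Let m be the share of admissions that fall after release and are missed. If these count as non-events, observed rate = true rate × (1 − m). The true rates and m are assumptions, because the protocol gives neither. The admission figures under Study setting (55.4%, 40% and 63.41%) are for all suspected cases, whereas the trial excludes patients needing admission at the first visit. The last column is the main-trial size per arm (two-sided 5%, 80% power, pooled variance):

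n = [1.96·√(2p̄(1−p̄)) + 0.842·√(p₁(1−p₁)+p₂(1−p₂))]² / (p₁−p₂)²

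| m in both arms | Observed rates | Difference | n per arm |
|---|---|---|---|
| 0 | 40% v 25% | 15 points | 152 |
| 10% | 36% v 22.5% | 13.5 points | 178 |
| 20% | 32% v 20% | 12 points | 209 |
| 30% | 28% v 17.5% | 10.5 points | 250 |

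The risk ratio is 1.6 in every row.

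**5. Effect of unequal loss.** With no true effect and a common true rate p, the spurious difference is p × (difference in m between arms). At p = 20%, a gap in m of 10 to 20 percentage points gives 0.20 × 0.10 = 2 points to 0.20 × 0.20 = 4 points. At p = 50% it gives 5 to 10 points. The sign depends on which arm is released earlier.

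**The case against.** The strongest case on the other side has five parts.

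- **Capture outside telephone tracing.** The clinic is part of the medical centre and stands in its grounds. Patients with fever of three days or more are listed at triage, and every participant has the warning signs read out. Figure 2 and the data collection form are not visible and might describe another route. This stands in part: a reader might infer that admissions after release are never found, and the document does not support that. It supports only that no route is described.
- **No classification rule.** A reader might also infer that the plan counts such patients as not hospitalised. It does not say so. That is the likely default of a crude proportion.
- **The phase label is a baseline descriptor.** True: it is assigned from the illness day at recruitment, and days 4 to 6 are nowhere called an observation window. The day ranges still show when the protocol places the critical phase, but applying them at release is an extension.
- **The two wordings on release barely differ.** Both leave the decision to the attending doctor, and in both either clinical or laboratory grounds suffice. This stands: it is loose wording, not two structurally different rules.
- **This is a small pilot, and early release may be rare.** The Background cites a mean fever of 5 days in ambulatory patients, which makes day 4 an extreme case, though it does not put release past day 6. At 30 per arm and 40% v 25%, the 95% half-width is 1.96 × √(0.24/30 + 0.1875/30) = 23 points, far wider than the 1.5 to 4.5 points lost in step 4. This lowers the priority. It does not remove the point, because testing the research process and estimating the effect size are stated objectives, and no later analysis can recover admissions that were never collected.

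**Conclusion.** The point holds as a gap in ascertainment. The protocol fixes no uniform window for hospitalisation and describes no check after release. Its rules permit release within illness days 4 to 6, so some admissions may be missed, with intravenous fluid need affected in the same way.

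The size cannot be computed from the document; the figures above rest on assumed rates and assumed shares missed. It is tempting to conclude that the observed between-arm difference must be too small. That follows only if some admissions are missed, are counted as non-events, and are lost about equally in both arms. With unequal loss the comparison could be biased in either direction. The change is a cheap improvement to a feasibility study, not the correction of a figure that is wrong.

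**What to change.** 1. Reconcile the wording of Screening and Duration on when follow-up ends. Which rule applies, and when a patient is released, stays with the clinical team.
2. Separately, and for outcome ascertainment only, define hospitalisation and intravenous fluid use over one fixed number of days from randomisation, the same for every participant. It should be long enough that the earliest recruits are observed past illness day 6: a patient randomised on day 3 reaches day 7 after 7 − 3 = 4 days, so the window cannot be shorter than that. Counting from randomisation matters, because an end set by illness day would give patients recruited on day 7 or later little or no window.
3. Extend the existing telephone procedure to all participants, once, at the end of that window. The online trace is no substitute as written, since it does not mention admissions. Calls for those recruited near the end of July will fall after the stated close of data collection on 30 July, so that date needs an allowance for this item.
4. Report participants who cannot be reached as unknown, by arm, and not as non-events.

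The cost is one short call per participant by existing research staff (at least 60 at the minimum size) and a few sentences in the protocol. Some participants will remain unreachable.

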## **Control group**

The researcher or the research assistant will obtain data regarding the twenty four hour fluid recall and the types of fluids consumed for each subsequent follow-up visit.

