Although there has been some evidence that encouraging oral fluid intake might decrease the morbidity of dengue infections, it is still uncertain whether oral fluid intake exerts a protective effect against the progression from non-severe to severe dengue . It is still unknown whether increasing oral fluid intake would alter the progression of dengue in terms of the degree of haemoconcentration and the fall in platelets.

Both of these parameters are routinely used for monitoring of both outpatients and hospitalized suspected dengue patients. Primary healthcare providers monitor these parameters very closely. Coupled with the clinical condition, primary physicians determine the necessity for hospital admission. Moreover, both these parameters constitute part of the warning signs mentioned in the WHO 2009 guidelines. However, it is still unknown whether increasing oral fluid intake in dengue patients will improve the mortality of dengue by lessening its progression or severity.

From the two studies looking at the effects of oral fluid intake, more questions arise. Should there be an association between oral fluid intake and the risk of hospitalization for dengue patients, an accurate estimation of the amount of fluid needed daily to achieve this effect is not known. The Nicaragua study collected data by retrospectively asking the patients how many glasses of fluid was ingested during the previous 24 hours. The findings are subject to recall bias. Moreover, there is a great variation in size of the glasses and cups used by the general population. Therefore an accurate estimate of the amount of fluid ingested daily could not be obtained.

The Taiwan study did not collect any data on the amount nor the type of oral fluids consumed by the patients in their oral hydration group. The only study that had some data on the types of fluids consumed by their patients was the study done in Nicaragua. Thus, little is known on the kinds of fluids that would be ideal for oral hydration in dengue patients. Such knowledge would greatly aid the primary healthcare members as well as other clinicians in providing accurate, evidence based advice regarding the quantity and types of fluids for dengue patients to consume in order to avoid hospitalization.

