# Aim

To assess the feasibility and acceptability of conducting a randomised controlled trial to evaluate the effectiveness of a fluid chart compared with 24 hour fluid recall to improve the oral fluid intake of suspected dengue patients in a primary care setting

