#### Method of intervention received by the control group only

Apart from this, the control group will be asked their twenty four hour fluid recall. This means that the patient will be asked to give an estimate of how much fluid they have drunk in the twenty four hours prior to the current consultation with the researcher or the trained research assistants.

This estimate will be given by the patients in terms of how many litres or millilitres of fluid they drank, how many glasses (small or large sized glasses or mugs), or how many bottles of drinks they had (500ml size, 1 litre size, or 1.5 litre size), or how many packet drinks they had. Details on what type of fluids is consumed orally will be obtained. This information will be obtained during recruitment of the patient, and on each subsequent follow-up.

One should take note that no fluid chart or cup will be given to the control group participants.

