#### Intervention group

The researcher or the research assistant will collect the fluid chart given previously and clarify with the patient regarding their entries on the fluid chart. After the patient's consultation with their respective doctors, the researcher or the assistant will give a new fluid chart to the patient if they had been given a another clinic appointment for outpatient monitoring.

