## Preliminary outcome measures

The outcomes will be assessed at the end of the two month period of data collection.

Several preliminary outcomes measures will be used to assess the trend of the preliminary results in order to determine the treatment effect size of the fluid chart. The two pilot study groups will be compared in terms of:

- 1. The hospitalization rates
- 2. The need for intravenous fluid treatment
- 3. The severity of haemoconcentration. Four surrogate endpoints were utilized to determine this, and they were as follows:
  - a. The mean peak haematocrit
  - b. The difference in haematocrit level between the values of clinic consultation 2 clinic consultation 1.
  - c. Those above the local cut off value of haematocrit indicative of plasma leakage.
  - d. Haematocrit fluctuation of 20% or more
- 4. With regards to assessing the severity of the platelet drop, two secondary endpoints were used:
  - a. The mean nadir platelet count
  - b. The difference in the platelet level between the values of clinic consultation 2 clinic consultation1.
- 5. The difference in the amount of oral fluid intake between the two groups.

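### Follow-up fluid intake is read from a written chart in one arm and from memory in the other, so the planned intake comparison cannot separate the chart's effect on drinking from the difference between instruments

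*Protocol*

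**What the plan says.** Control arm. Under the control-only intervention heading, "the patient will be asked to give an estimate of how much fluid they have drunk in the twenty four hours prior", in whatever containers the patient names, and "no fluid chart or cup will be given to the control group participants". At follow-up, staff "will obtain data regarding the twenty four hour fluid recall and the types of fluids consumed for each subsequent follow-up visit". The section on conversions for total fluid intake turns these reports into millilitres with assumed volumes, for example 175 ml for every home glass and 250 ml for a mug or large cup.

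Intervention arm. Patients get a uniform cup holding up to 175 ml and write down the time, amount and type of each drink. At follow-up, staff "will collect the fluid chart given previously and clarify with the patient regarding their entries on the fluid chart".

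Use of the data. The fifth item under Preliminary outcome measures is "The difference in the amount of oral fluid intake between the two groups". That section says the outcomes serve "to assess the trend of the preliminary results in order to determine the treatment effect size of the fluid chart". The Statistical analysis section applies a Student's t test with p < 0.05 as the threshold.

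The protocol's view of recall. Of an earlier study that asked patients how many glasses they had drunk in the previous 24 hours, the Background says: "The findings are subject to recall bias". It adds that glass sizes vary widely and that no accurate daily amount could be derived.

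**The concern.** The chart is both the treatment in one arm and the ruler by which that arm's outcome is read. The other arm is read with a different ruler, one that the protocol considers unreliable. An error shared by both arms would largely cancel in the difference, whereas an error confined to one arm becomes bias. If recall misses drinks that the chart captures, the chart appears to raise intake when nobody drank more. If charts are filled in incompletely, a real gain is hidden.

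This is a matter of data collection, so no later analysis plan can repair it. A larger sample would only estimate the mixed quantity more precisely. At stake is the meaning of the intake difference, and the main trial's sample size if that difference is carried forward as the effect size.

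**Working it through.** **Step 1: the instruments side by side (follow-up, outcome 5).**

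| Feature | Control | Intervention |
|---|---|---|
| Source of the amount | memory, at the visit | written record, drink by drink |
| Container | the patient's own, assumed volume | supplied cup, measured, up to 175 ml |
| Other arm's instrument also used? | no chart or cup | no recall described |

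The follow-up section for both groups lists blood tests and temperature. It names no shared intake measure. No calibration of one instrument against the other is described.

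**Step 2: what the comparison estimates.** Let T be the true effect of the chart on daily intake, c the mean error of the chart and r the mean error of recall. The expected between-arm difference is

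D = T + (c − r).

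Each arm supplies only one kind of reading, so T and (c − r) cannot be told apart. Nothing here depends on the time window: if the next visit is one day later and both instruments cover the same 24 hours, (c − r) is still there. If the next visit is several days later, the chart covers the whole interval and recall only the last day, which is a separate, additional mismatch.

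**Step 3: the plan's own figure.** The stated minimum is 30 per arm, and 2 × 30 = 60 agrees with the stated total. It rests on no effect size, SD or power, so there is no power calculation to reproduce.

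**Step 4: illustration only.** From the protocol: n = 30 per arm, Student's t test, threshold 0.05 (two-sided assumed). Assumed, with no source in the protocol: T = 0, true intake 2,000 ml/day in both arms, SD 700 ml/day, and recall reading 10%, 20% or 30% below the chart (200, 400 or 600 ml/day).

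SE = SD × √(2/n) = 700 × √(2/30) = 180.7 ml; 58 degrees of freedom; critical value 2.00; noncentrality = gap / SE.

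| Gap (ml/day) | SD (ml) | Noncentrality | Chance of p < 0.05 |
|---|---|---|---|
| 0 | 700 | 0 | 5% |
| 200 | 700 | 1.11 | 19% |
| 400 | 700 | 2.21 | 59% |
| 600 | 700 | 3.32 | 90% |
| 400 | 500 | 3.10 | 86% |
| 400 | 900 | 1.72 | 40% |

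**Step 5: effect on the main trial, if intake were used to size it.** Assume T = 300 ml/day, SD 750 ml, 80% power and two-sided 5%. With n per arm = 2 × (1.96 + 0.84)² × SD² / D²:

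- D = 300 (no instrument gap): 99 per arm.
- D = 500 (gap adds 200): 36 per arm.
- D = 100 (gap removes 200): 883 per arm.

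The instrument gap alone can therefore leave the main trial far too small or far too large.

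**The case against.** **The contrast is deliberate.** The Aim is "to evaluate the effectiveness of a fluid chart compared with 24 hour fluid recall to improve the oral fluid intake", so recall is the named comparator procedure. That justifies giving the arms different procedures. It does not justify reading the outcome from them, because an improvement in intake has to be read on one scale.

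**This is a pilot.** It tests feasibility, including the cup as a standard measure, and one objective is to refine the process. A measurement problem is partly what a pilot exists to reveal. This lowers the stakes, but a confounding visible beforehand need not wait for the data.

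**The reach is limited.** This stands. A reader might infer that the main trial will be sized on a biased intake figure. The protocol does not say so: the Study objectives, Preliminary outcome measures and Estimated sample size sections name no outcome for that purpose, and hospitalisation is listed first. Hospitalisation, need for intravenous fluid, haematocrit and platelets are not oral intake readings. (The chart does have a column for intravenous bottles, but the protocol does not say that the intravenous fluid outcome is taken from it.)

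**The percentages are hypothetical.** This also stands. They show what a gap of a given size would do, not that this trial has such a gap. The protocol's own volumes are sometimes used to suggest one: five home glasses of 250 ml counted at 175 ml lose 5 × 75 = 375 ml. But the protocol converts mugs and large cups separately at 250 ml, so that is a question about container conversion rather than evidence of recall error.

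**Recall may be taken in the intervention arm.** The flow diagram and data collection form are not available here, so the supportable wording is that none is described.

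**Unblinded staff clarify the chart entries.** The same unblinded staff elicit the control recall, and the protocol declares the lack of blinding openly. The documents do not show that this acts differently in the two arms.

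**Conclusion.** The point holds for preliminary outcome 5. As the protocol is written, arm and instrument coincide completely at follow-up, and the intake difference mixes the chart's effect on drinking with chart-minus-recall error. This follows from the text and rests on no numerical assumption. The size and direction of the error are unknown; the percentages and sample sizes shown depend on an assumed SD, instrument gap and true effect.

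Three stronger conclusions are not supported: that the pilot will show a false benefit (the bias may run either way), that the main trial will necessarily be mis-sized (only if intake is the effect carried forward), and that a common recall would yield a clean estimate of the chart's effect (some confounding would remain).

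**What to change.** At each follow-up visit, put the same scripted 24-hour recall to both arms, with the same container list and conversions. Take it from intervention patients before they hand over the chart. Use this recall for outcome 5 and for any intake effect size. Keep the chart as the intervention and as a process measure, and report chart minus recall over the same 24 hours in the intervention arm as descriptive only, since recall error among chart-keepers may not carry over to controls.

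State the limits in the protocol. Keeping a chart and drinking from a cup of known volume may sharpen recall in that arm, while controls still report home containers at assumed volumes, so the confounding is reduced and not removed. Recall is also noisier than a chart.

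If no common recall is collected, state that the intake difference will not be interpreted as the chart's effect or used to size the main trial.

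Cost: a few minutes per follow-up visit in the intervention arm with existing staff, one extra field on the data form, and a change of protocol wording. The alternative costs only the wording.
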